#### Categorical data:

In terms of clinical cure, the Mantel-Haenszel Chi-Square trend test will be performed between planned dose (in mg/kg) and response frequency, for each treatment administered, i.e.:

- Biltiricide®
- rac-PZQ ODT
- L-PZQ ODT

Similar trend tests will also be applied to actual dose, where actual dose will be categorised as follows:

- Less than 30 mg/kg
- 30 40 mg/kg
- 40 50 mg/kg
- 50 60 mg/kg
- 60 70 mg/kg
- More than 70 mg/kg

Again, results will be grouped by:

- Biltiricide®
- rac-PZQ ODT
- L-PZQ ODT

Trend test results will be tabulated. In addition, forest plots of response against planned dose will be presented by treatment administered, as listed above.

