Reference therapy	Rac-PZQ oral tablets (Biltricide® 600 mg) in crushed form					
	Mode of administration: the tablets (scored) will be divided into 150 mg parts, crushed, suspended in water and the solution will be swallowed after a meal.					
	Doses: 20 mg/kg t.i.d. dose given every 4 hours (cohort C1) and 40 mg/kg single dose (cohort C2)					
Planned trial and treatment duration per subject	Maximum 28 days of pre-screening and screening period, followed by 1 day treatment and 14-21 days of follow-up period.					
	Total duration per subject: up to 7 weeks.					
Statistical methods	All efficacy and safety endpoints will be analysed descriptively. Point estimation and 95% confidence interval (CI) will be calculated for primary and secondary efficacy endpoints for each treatment					

arm. The calculation of 95% CIs for proportions will rely on the Clopper-Pearson (exact) method.

The primary efficacy endpoint will be presented as cure rate (Kato-Katz method). For each treatment arm, the cure rate will correspond to the percentage of subjects becoming egg-negative 14-21 days after treatment with the study drug. Criteria for dose selection will be described in a SAP prior to first patient first dose.

Secondary endpoints will be described by treatment arms:

- Mean Egg Reduction Rate (ERR, %) 14-21 days after treatment (Kato-Katz method)
- Cure rate (POC-CCA method) as assessed by the absence of parasite antigens as determined in urine with the commercially available POC-CCA assay for *S. mansoni*

Sample size estimation

This study is exploratory. There is no null hypothesis tested.

Part 1: the sample size is based on the precision of the 95% CI of the cure rate (Kato-Katz method) in each arm. A cure rate of 70% is considered as the minimum-clinically meaningful threshold. A sample size of 50 evaluable subjects provides a probability of around 85% to observe a cure rate of \geq 70%, if the overall true cure rate is 75% (assuming 40% of moderate/heavy and 60% of light infections). Assuming an approximately 17% dropout rate, 60 subjects per arm will be randomized to ensure at least 50 evaluable subjects per arm.

Part 2: 30 subjects aged 13 to 24 months infected with *S. mansoni* (C8) and 10 subjects aged 3 to 12 months infected with *S. mansoni* (C9) will be included to evaluate drug tolerability and efficacy.

2 Sponsor, Investigators and Trial Administrative Structure

This clinical trial will be sponsored by:

Merck KGaA

[name]

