## 10.2.1 Subgroup definition and parameterization

Subgroup analyses will be performed on subgroups as defined below.

The final parameterization will be updated and fixed at the Data Review Meeting at the latest and documented in an amendment to this SAP if different from the following definition.

The following subgroups will be defined:

- Age (some age ranges may not be applicable, depending on certain trial adaptations) Part 1:
  - 2 years  $\leq$  age < 4 years
  - 4 years ≤ age ≤ 6 years (Ref) Part 2:
  - 3 months  $\leq$  age < 13 months
  - 13 months  $\leq$  age < 24 months (Ref)
- Gender
  - Male (Ref)
  - Female
- Severity of infection (as assessed at Pre-screening [D-28 to D-1])
  - S. mansoni infection
    - Light infection: 1 99 eggs per gram of faeces (Ref)
    - $\circ$  Moderate/heavy infection:  $\geq 100$  eggs per gram of feaces
- Treatment group
  - Biltricide® 3x20mg/kg t.i.d
  - Biltricide® 40mg/kg single dose (Ref)
  - rac-PZQ ODT 1x40mg/kg single dose
  - rac-PZQ ODT 1x60mg/kg single dose
  - L-PZQ ODT 1x30mg/kg single dose
  - L-PZQ ODT 1x45mg/kg single dose
  - L-PZQ ODT 1x60mg/kg single dose
- Trial center/country
  - PPD
  - PPD

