### Exposure, in terms of dosing, will be derived as follows:

• Exposure:

{Cumulative Actual Dose [mg]}

If *Actual Dose* is missing, exposure will be derived as {Cumulative *Planned Dose* [mg]}, which will be flagged in listings

• Exposure with respect to weight:

{Cumulative Actual Dose [mg]} / weight [kg], as calculated using the weight measurement at dosing

If *Actual Dose* is missing, exposure will be derived as {Cumulative *Planned Dose* [mg/kg]}, which will be flagged in listings

Handling of other missing data:

• In case the start date is missing, it is assumed that the first dose of trial medication is given at the randomisation date. The randomisation date will replace incomplete dates of the first dose of trial medications.

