### Clinical cure rate by subgroup:

Again, analyses will be based on responders, which will be defined as was done in section 16.1.1 of this SAP. If the End of Study Kato-Katz egg count is missing, it will be imputed using the LOCF approach. Subgroup analyses of Part 1 and Part 2 of the study will be performed separately, by the following subgroups:

- Age category
- Gender
- Severity of infection
- Trial site (if applicable, i.e. more than one site)

Descriptive statistics of cure rates for each subgroup, individually and all in combination (four-way), will be estimated for each cohort using PROC FREQ.

Subgroup analysis will be performed utilising logistic regression to model clinical cure, i.e. *response* on gender, age category, severity of infection, day of assessment (e.g., Day 14-21), dose, formulation (ODT or not) and active pharmaceutical ingredient (L-PZQ or not [i.e. rac-PZQ]). The analysis will be repeated and presented separately for planned dose (mg/kg) *vs.* actual dose with respect to body weight (mg/kg) and actual dose in mg. Definitions and reference levels of subgroups are described in section 10.2.1 of this SAP. The PROC LOGISTIC procedure in SAS will be used with appropriate DESCENDING (to model on *response*=1) and PARAM=REF

(dummy coding for parameter estimates) statements to determine odds ratio point estimates and corresponding 95% Wald CIs.

To compliment PROC LOGISTIC results, the diagnostic plots using Pearson residuals will be produced [PLOTS(ONLY LABEL)=(INFLUENCE)].

Cure rate, in terms of proportion of responders, will be summarised by cohort (and by infection severity), and listed by cohort and subject. Estimates of cure rate will be presented graphically in the form of a forest plots presenting means and 95% CIs, by subgroup and cohort. For logistic regression results, odds ratio point estimates of model parameters and corresponding 95% CIs will be presented for each parameter, by cohort. Dose-response curves will be presented for the different active pharmaceutical ingredients (rac-PZQ/L-PZQ), separated by severity of infection, as well as pooled (all infections). Dose response curves will be generated for planned dose (in mg/kg), actual dose with respect to weight (in mg/kg) and actual dose in mg. These summary tables will be followed by the respective diagnostic plots.

Results will be presented for each analysis set.

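### The Biltricide dose trend compares two regimens that differ in schedule as well as dose, and the pooled logistic model has no schedule term to separate the two

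*SAP*

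**What the plan says.** The Protocol synopsis (Reference therapy) gives the Biltricide regimens as "20 mg/kg t.i.d. dose given every 4 hours (cohort C1) and 40 mg/kg single dose (cohort C2"). SAP 10.2.1 labels the first "Biltricide® 3x20mg/kg t.i.d" and makes the single dose the reference group.

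Three planned outputs use these arms as points on a dose scale:

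- **SAP 16.3.2, categorical data.** For Biltricide, rac-PZQ ODT and L-PZQ ODT separately, "the Mantel-Haenszel Chi-Square trend test will be performed between planned dose (in mg/kg) and response frequency". Similar trend tests follow on banded actual dose. The continuous-data part of the section adds Pearson correlations between dose and individual egg reduction, again by product.
- **SAP 16.1.2, logistic model for cure.** Besides gender, age category, severity and day of assessment, the terms are "dose, formulation (ODT or not) and active pharmaceutical ingredient". No schedule term is listed. On the dose variable: "The analysis will be repeated and presented separately for planned dose (mg/kg"), and again for actual mg/kg and actual mg.
- **SAP 16.1.2, curves.** "Dose-response curves will be presented for the different active pharmaceutical ingredients (rac-PZQ/L-PZQ"). The rac-PZQ curve therefore takes in C1 along with the single-dose arms C2 to C4.

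SAP 15 totals dose cumulatively, with the per-kilogram version "as calculated using the weight measurement at dosing". That implies a nominal 3 x 20 = 60 mg/kg for C1. Neither 16.1.2 nor 16.3.2 states the planned-dose score for C1.

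**The concern.** A trend test or a slope labelled dose is read as the effect of giving more drug. In the Biltricide comparison, the arm with the larger daily total also receives it in three divided administrations. A difference in cure could come from the total, the schedule or both, and two arms cannot tell them apart.

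In the logistic model the same arm enters a slope shared with the ODT arms. It also makes up half of the non-ODT comparison group, which is only C1 and C2. A schedule effect would therefore appear partly as a dose effect and partly as a difference between ODT and crushed tablet. Under SAP section 5 these analyses go into the clinical study report and may be used in submissions or manuscripts, where the labels would be taken at face value.

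**Working it through.** **Inputs.** Arms and doses are from SAP 6.1: C1 20 mg/kg t.i.d., C2 40, C3 40 (ODT), C4 60 (ODT), and L-PZQ ODT C5 30, C6 45 and C7 60 mg/kg. There are 60 subjects per arm (SAP 7.1) and C7 is optional. The documents give no schedule effect and no numerical test level. The effect sizes below are assumptions, and 0.05 two-sided is assumed to match the 95% intervals.

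**The plan's own figure.** The documents give no figure for the trend test or the logistic model. The nearest is the probability of about 85% of observing at least 70% cure with N = 50. Summing Bin(30, 0.85) and Bin(20, 0.60), P(X >= 35) = 84.7%, which reproduces it.

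**Step 1: the Biltricide trend.** The statistic is (N - 1)r², where r is the correlation between dose score and cure. With two groups, rescoring can change only the sign of r. Take 48/60 cured in C1 and 42/60 in C2 as an example. Then |r| = 0.1155 and the statistic is 119 x 0.01333 = 1.587, for scores 60/40, 20/40 or 1/0 alike. Intercept, dose and schedule are three parameters, but two arms give rank 2, so the aliasing is complete at any sample size. With no dose effect, 75% cure in C2 and an assumed t.i.d. odds ratio of 1.5, 2 or 3, the test would declare a trend about 15%, 31% or 58% of the time.

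The actual-dose version mixes schedules within bands. If each administration is rounded to the closest 150 mg, a 10 kg child gets 3 x 150 = 450 mg in C1 and 450 mg in C2, or 45 mg/kg in both.

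**Step 2: the logistic model.** Model: logit P(cure) = a + b(dose/20) + c(ODT) + d(L-PZQ), fitted to expected counts with the demographic and severity covariates and day of assessment left out. Assumed truth: 85% cure in C1, 70% in every other arm, no dose or ODT effect. The implied t.i.d. odds ratio is (0.85/0.15)/(0.70/0.30) = 2.43.

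| C1 score | C7 | Dose OR per 20 mg/kg (95% CI) | ODT OR (95% CI) |
|---|---|---|---|
| 60 | yes | 1.19 (0.81 to 1.76) | 0.68 (0.38 to 1.21) |
| 60 | no | 1.35 (0.81 to 2.24) | 0.68 (0.38 to 1.21) |
| 20 | yes | 0.84 (0.57 to 1.24) | 0.81 (0.40 to 1.62) |
| 20 | no | 0.74 (0.45 to 1.23) | 0.91 (0.42 to 1.96) |

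Both odds ratios should be 1.00. Every interval includes 1. The bias scales with the assumed effect: with C1 scored 60, C7 included and 75% base cure, t.i.d. odds ratios of 1.5, 2 and 3 give dose odds ratios of 1.09, 1.15 and 1.22 and ODT odds ratios of 0.83, 0.73 and 0.64. A t.i.d. odds ratio of 0.5 reverses both (0.83 and 1.45).

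**Step 3: with a t.i.d. indicator.** The design has full rank (5 columns, with or without C7), because the ODT arms identify the slope if it is common to all products. Dose and ODT odds ratios return to 1.00 in all four rows. Leaving C1 out gives the same.

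**The case against.** The strongest reply is that little depends on these outputs. SAP section 11 calls all tests exploratory, 16.1.2 is headed as supportive, and 16.3.2 sits under other endpoints. That stands, and it limits the weight of the point. It does not make a coefficient labelled dose or ODT mean what its label says.

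Two stronger readings are tempting, and the documents support neither:

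- A reader might infer that the choice of formulation is distorted. Both candidates are ODTs, so the ODT-or-not coefficient cannot favour one over the other. The L-PZQ coefficient could, but in the table's first row it moves only to 1.05 (1.20 without C7, interval about 0.6 to 2.3). The efficacy criterion in SAP 7.1 is an observed cure rate above 70% in the arm itself, which C1 cannot affect.
- A reader might infer that the dose-response objective is compromised. Protocol 4.2 names only the two ODTs for Part 1, and their own trend tests in 16.3.2 do not include C1. Only the pooled slope and the rac-PZQ curve are exposed.

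A reader might also make much of a trend whose sign depends on scoring C1 as 60 or 20. The named statistic is an unsigned chi-square, and SAP 15 points to the cumulative total. The score still needs stating, because it does change the logistic slope.

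Finally, SAP 10.2.1 defines treatment group with C1 as its own level, which would absorb a schedule effect if it were in the model. It is not among the terms listed in 16.1.2.

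**Conclusion.** The point holds in a limited form. In the Biltricide planned-dose trend, dose and schedule are completely aliased, whatever the data. In the logistic model the problem is omitted-variable bias: conditional on a schedule effect, partial, and removable. In the worked example the spurious dose odds ratio runs from 0.74 to 1.35 and the ODT odds ratio from 0.68 to 0.91, depending on the score for C1 and on whether C7 is included.

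These figures rest on an assumed 15-point schedule effect that no passage supports, on expected counts at 60 per arm, and on a model pooled across cohorts without the other covariates. If schedule has no effect, there is no bias. The per-arm cure rates with exact intervals, the selection criterion, the ODT-specific trend tests and the choice between the two ODTs do not depend on it. Nothing here judges either regimen clinically.

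**What to change.** In the SAP:

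1. In 16.3.2, replace the Biltricide trend tests with a descriptive C1 versus C2 regimen comparison. Keep the two ODT trend tests.
2. In 16.1.2, add a t.i.d. indicator for C1 to the logistic model, or fit the model without C1.
3. Show C1 as a separate point or series on the rac-PZQ dose-response curve.
4. State the planned-dose score used for C1. SAP 15 implies the cumulative total.

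This takes SAP wording and one model term, with no new data. The price is some precision: in the worked example with C7 and C1 scored 60, the standard error of the ODT log odds ratio rises from 0.30 to 0.36, and that of the dose log odds ratio per 20 mg/kg from 0.20 to 0.22.

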#### 17 Safety Evaluation

The safety endpoints are:

- Changes in laboratory safety parameters and vital signs (body temperature, blood pressure and pulse rate)
- Occurrence, nature, severity and outcome of adverse events
- Occurrence of Adverse Drug Reactions per treatment group

#### Analysis set(s):

• SAF analysis set.

Safety analyses will be done on the safety analysis set and according to the as-treated principle. The subsections in this section include specifications for summarizing safety endpoints that are common across clinical trials such as AEs, laboratory tests, and vital signs.

### 17.1 Adverse Events

Details on AEs will be recorded on eCRF page "Adverse Events Details". Treatment-emergent adverse events (TEAEs) will be defined as those events with onset dates occurring after first IMP administration or events that worsen after first IMP administration.

All analyses described in Section 17.1 will be based on TEAEs if not otherwise specified.

Incomplete AE-related dates will be handled as described in section 11 of this SAP. Further information after cut-off (like fatal outcome) might be taken from Safety data base and included separately into CSR.

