3.4.2.2 Safety and tolerability data

A recent meta-analysis on comparative clinical trials where PZQ had been given to pre-school children showed no major safety findings in 1167 pre-school and school-aged children treated with PZQ at 40 mg/kg [11]. A study conducted in Niger in pre-school aged children reported that 34.2% (95% CI, 28.2% - 40.2%) of the pre-school children had experienced an adverse event within 24 hours from PZQ dosing but most of the adverse events occurred within 4 hours after drug administration [13] (Table 4). The most frequent adverse events in pre-school children were drowsiness (29.1%; 95% CI, 28.0% - 30.1%), dizziness (22.4%; 95% CI, 1.3% - 33.9%), fatigue (13.3%; 95% CI, 0.9% - 20.9%) and abdominal pain (13.1%; 95% CI, 3.0% - 30.6%). School aged children had higher frequency of treatment-emergent adverse events, i.e. drowsiness, nausea, abdominal pain, headache and diarrhoea, compared to pre-school children while pre-school had higher frequency in dizziness compared to school-aged children (Table 4).

		Pre-scho			School-aged					
			(bo	Incidence otstrap 95				Incidence (bootstrap 95%CI)		
Adverse event	Number of study arms	Number of subjects	%	Lower bound	Upper bound	Number of study arms	Number of subjects	%	Lower bound	Upper bound
Any adverse event	1	243	34.2	28.2	40.2	9	1342	57.8	44.7	72.0
Drowsiness	2	503	29.1	28.0	30.1	2	285	42.4	35.8	49.0
Dizziness	3	737	22.4	1.3	33.9	13	2812	9.1	4.6	13.8
Fatigue	3	737	13.3	0.9	20.9	3	781	13.2	0.4	28.9
Abdominal pain	4	980	13.1	3.0	30.6	18	3175	33.3	22.5	45.6
Itching/rash	2	503	8.6	8.0	9.1	8	1504	5.5	2.3	9.3
Nausea	3	737	7.8	2.1	12.6	12	2738	13.1	5.9	21.7
Diarrhoea	4	980	7.3	2.6	16.2	15	2786	11.8	5.2	19.5
Vomiting	4	980	6.9	1.7	9.6	14	2591	8.2	3.6	14.5
Headache	3	737	4.4	0.4	6.7	16	2994	16.6	9.8	24.0

Table 4. Adverse event incidence within 24 hours by children age group, PZQ 40 mg/kg (courtesy of [name] - personal communication).

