#### Handling of missing data:

Unless otherwise specified, missing data will not be replaced.

In all subject data listing, imputed values will be presented. In all listings, imputed information will be flagged.

Missing statistics, e.g. when they cannot be calculated, should be presented as "nd". For example, if n=1, the measure of variability (SD) cannot be computed and should be presented as "nd".

Where tables are presented over time, the total of missing and non-missing observations at each time-point should reflect the population still in the trial at that time. This does not apply when imputations are made beyond trial withdrawal. For example, if a subject is still in the trial at the time-point but with missing data, it should be counted in the number of missing observations.

Trial day / Treatment day are defined relative to the date of start of treatment. Trial day 1 defines the day of randomisation, the day before is defined as Trial day -1 (no Trial day 0 is defined). Treatment day will be calculated accordingly, i.e. treatment day 1 is defined as the date of first administration of IMP to any one of the study cohorts, C1-C9. Treatment duration will be one day only.

If required for an analysis, incomplete date or date/time fields will be imputed as follows:

- Missing start dates will default to the first day of the month and first month of the year, if month is missing, subject to the following exceptions:
  - If and AE/concomitant medication/procedure start date is missing and month is the same as the month of IMP administration, then the start date will default to the IMP start date. If the month is different, the start date will default to the first day of the month.
  - If start date and month is missing and stop date is not before first IMP administration, then the start date will default to the IMP start date.
  - If start date and month and stop date is missing, then the start date will default to the IMP start date.
  - Missing start dates for medical history and medications stopped prior to IMP administration will not be imputed.
- Missing stop dates will default to the last day of the month and last month of the year, if month is missing, subject to the following exceptions:
  - If stop date is missing for a known medical history/previous medication, then the stop date will default to the IMP start date 1 day.

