  - If stop date and month is missing for a known medical history/prior medication, then the stop date will default to the IMP start date 1 day.
  - If the stop date and month for a concomitant medication or AE is missing, it will default to the day of last contact with the participant.
- Unknown times will default to 00:00, subject to the following:
  - If an AE/concomitant medication/procedure start time is missing and day and month is the same as the date of IMP administration, then the start time will default to the IMP start time. If the day or month is different, the start time will default to 00:00.
  - If start time, date and month is missing and stop date is not before first IMP administration, then the start date/time will default to the IMP start date/time.
  - If start time, date and month and stop date is missing, then the start date/time will default to the IMP start date/time.
  - Missing start dates for medical history and medications stopped prior to IMP administration will not be imputed.
- Missing years will not be imputed.

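### SAP 17.1 counts only AE onsets after first dosing, but SAP section 11 sets some incomplete onsets equal to the dose, so those events fall outside the TEAE definition

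*SAP*

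**What the plan says.** **Definition.** SAP 17.1 has two limbs. An event is treatment-emergent if it is among "those events with onset dates occurring after first IMP administration", or among "events that worsen after first IMP administration". The scope is wide: "All analyses described in Section 17.1 will be based on TEAEs if not otherwise specified". The listings in SAP 17.1.1 are also lists of TEAEs and serious TEAEs.

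**Incomplete onsets.** SAP 17.1 sends incomplete AE dates to SAP section 11 (Handling of missing data), which sets:

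- day missing, month the same as the dosing month: "then the start date will default to the IMP start date";
- time missing, day and month the same as dosing: "then the start time will default to the IMP start time";
- time, day and month all missing, with a stop date that is either missing or not before dosing: "then the start date/time will default to the IMP start date/time";
- time missing on any other day: "If the day or month is different, the start time will default to 00:00".

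**Timing of events.** Treatment lasts one day. Protocol 3.4.2.2 says of one cited study in pre-school children that "most of the adverse events occurred within 4 hours after drug administration". Another study cited in the same section puts three quarters of events in that window. Protocol 6.5.5 likewise expects most events straight after dosing.

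**The concern.** The definition uses a strict *after*, while the imputation places certain events exactly at the dose. An event at the same moment as the dose is not after it, so the two rules together exclude the events that the imputation was evidently meant to keep. The second limb does not help, because a new event with an unknown onset has nothing to worsen from.

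This also runs against how the SAP treats other missing AE attributes. Under SAP 17.1.1 a missing severity is taken as the greatest and a missing relationship as the strongest. For a missing onset alone, the literal result is that the event disappears.

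The definition is also silent on the unit of comparison. It speaks of onset *dates* but compares them with an administration, which has a clock time. In a one-day treatment with mostly early reactions, the choice matters.

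What is at stake is the AE summary by cohort, by treatment, by severity and by relationship. An acceptable safety profile is part of the Part 1 primary objective.

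**Working it through.** The plan gives no figure to reproduce here. The check applies the definition to test cases and then shows an illustrative size.

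**Step 1. Apply the rule.** Take a dose at 09:00 on Day 1 (an arbitrary time for illustration). Complete each onset by SAP section 11, then ask whether the event is a TEAE under four possible codings.

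| Event | Onset used | Date > | Date ≥ | Date/time > | Date/time ≥ |
|---|---|---|---|---|---|
| Recorded before dosing | Day 1 08:00 | no | yes | no | no |
| Recorded after dosing | Day 1 11:00 | no | yes | yes | yes |
| Day 1, time missing | Day 1 09:00 | no | yes | **no** | yes |
| Start wholly missing | Day 1 09:00 | no | yes | **no** | yes |
| Day 2, time missing | Day 2 00:00 | yes | yes | yes | yes |

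An onset with the day missing in the dosing month ties by date. If its time is also missing and the time rule is then applied to the completed date, it ties to the minute and behaves like the third row.

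Reading the columns:

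- **Date >** loses every new Day 1 event.
- **Date/time >** keeps events with a recorded post-dose time and loses only the ties.
- **Date ≥** keeps all post-dose events but wrongly takes in the recorded pre-dose event.
- **Date/time ≥** classifies all five cases sensibly.

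**Step 2. Illustrative size.** Inputs: 60 subjects per Part 1 cohort (SAP 6.1); 34.2% of pre-school children with an AE within 24 hours in one cited study, and three quarters of AEs within 4 hours in another (both Protocol 3.4.2.2).

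- Subjects per cohort with an AE within 24 hours: 60 × 0.342 = 20.5.
- Of these, with onset within 4 hours: 20.5 × 0.75 = 15.4. Dosing is in the morning (Protocol 7.1.3), so these onsets fall on Day 1.
- Strict date-only coding: about 15 or more subjects per cohort at risk of being missed.
- Strict date/time coding: if a share *m* of onsets lacks a time, about 20.5 × *m* subjects. For *m* = 5%, 20.5 × 0.05 = 1.0. For *m* = 20%, 20.5 × 0.20 = 4.1.

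The values of *m* are assumed, because the documents give no rate of missing onset times. The arithmetic treats each affected subject as having one event, and applies a share of events as if it were a share of subjects. It shows an order of magnitude only.

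**The case against.** The strongest reply is that a date/time comparison is plainly meant. SAP 17.1 compares onset with the administration, not with its calendar date. Where the SAP wants a calendar-date rule it says so, as for medications in SAP section 14. Protocol 7.4.1.2 requires onset times, Appendix II schedules AE assessments from half an hour after dosing, and rules for imputing AE start times would have little use if only dates were compared. A programmer would probably treat the imputed ties as treatment-emergent, and the data review meeting (SAP 8.4) is a chance to confirm it. Reactions to administration are also tabulated separately without a TEAE filter (SAP 17.6), and Protocol 8.5.4 has all safety variables listed by subject and time point.

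Much of this stands, and it rules out three stronger readings that a reader might infer:

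- **Acute events in general are dropped.** This needs a date-only comparison, which is the less natural reading. Under date/time, an event with a recorded post-dose time is counted.
- **Every event with an imputed onset is lost.** SAP section 11 sets a missing time on another day to midnight, and a missing day in another month to the first of that month. An event placed in this way on a day after dosing remains a TEAE.
- **The C7 decision was affected.** SAP 8.1 describes that review as a separate summary of acute AEs, with outputs specified in the SMC charter, which is not among the documents. A page header dates this SAP version 31 January 2018, and the protocol synopsis gives December 2017 as the end of Part 1 enrolment. This wording therefore cannot be shown to have governed that decision.

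The tie itself remains. An evident purpose is not a stated rule, and the reaction tables cover only responses seen directly at dosing.

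**Conclusion.** The point holds for tied onsets. SAP 17.1 and section 11, each followed as written, together exclude new events whose onset is set to the IMP start. This is so under a strict comparison by date/time, and by date the loss is wider. The excluded events would be missing from the section 17.1 tables and from the TEAE listings.

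The size under the probable date/time reading is unknown. The range of about 1 to 4 subjects per cohort of 60 rests on an assumed 5% to 20% of onsets lacking a time and on a 24-hour AE incidence borrowed from one cited study. If onset times are recorded completely, as the protocol requires, the loss from imputation is nil. The figure of about 15 per cohort applies only if the comparison is coded by date, which the SAP does not state and probably does not intend.

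This is a gap in a definition that could distort the safety tables. It is not evidence that any decision in the trial was wrong. It merits correction because the wording governs every AE summary in section 17.1 and the remedy is small.

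**What to change.** Replace the definition in SAP 17.1 with one that states three things:

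1. A TEAE is an event with onset date/time at or after the date/time of first IMP administration, or one that worsens thereafter.
2. An onset that section 11 imputes to the IMP start date or time counts as treatment-emergent.
3. An event with a recorded pre-dose onset on Day 1 is not a TEAE unless it worsens after dosing.

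The third item is needed because Appendix II also collects AEs at the Day 1 pre-dose visit. A plain rule of onset on or after the dosing date would count those events as treatment-emergent.

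Section 11 already makes a wholly missing start conditional on the stop date not preceding dosing. Applying the same condition to the other two imputed cases would keep out events known to have ended before the dose.

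The cost is a sentence or two in the SAP and a matching line in the programming specification. No new data are needed. Reporting the number of AEs with imputed onset, by cohort, would show how much the rule matters.
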